### **8.1.1 Treatment Emergent Adverse Events**

TEAE is defined as an adverse event reported during the treatment emergent period (defined in Section 4.1.6). Any ongoing event that worsens in severity after the first dose date of study drug is also defined as a TEAE. Incomplete onset dates will be imputed as detailed in Section 4.2, for the purpose of determining whether AEs are treatment emergent.

TEAEs will be tabulated in summary tables by treatment arm. For each treatment arm, frequency and percentage of adverse events within each system organ class and preferred term will be presented. The denominator for the adverse event incidence will be based on the number of safety population subjects in that treatment arm, unless otherwise specified. Adverse event incidence rates will also be summarized by severity and relationship to study drug based on the investigator’s judgment.

Subjects with multiple occurrences of events for a given preferred term, system organ class, or overall will be counted only once at the maximum severity and strongest relationship to study drug, respectively, for each preferred term and system organ class.

In addition, Grade 3 or Grade 4 TEAEs, TEAEs that led to permanent study drug discontinuation, TEAEs that led to dose reduction, TEAEs that led to dose interruption, serious TEAEs, and TEAEs that resulted in death will be summarized by treatment arm as treated.

### **8.1.2 Adverse Events of Clinical Interest**

Adverse events of clinical interest (ECIs) are specified in Appendix 1 and are to be reported for the duration of study treatment and during any protocol-specified follow-up periods, including post-disease progression phase for overall survival. These events will be summarized similarly to TEAEs by treatment arm.

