The Post-disease Progression Phase will begin once the IRC has confirmed that a subject has progressive disease. In this phase, subsequent anticancer therapy with start date of therapy, IWCLL indication for treatment initiation, additional malignancy occurrence, and subject survival status will be recorded. The Post-disease Progression Phase will continue until death, lost to follow up, consent withdrawal, or study closure, whichever occurs first. Survival status must be assessed, and the date of death must be documented for each subject randomized to treatment, regardless of whether or not the subject received treatment.

Assessment of response and progression will be conducted in accordance with the IWCLL 2008 criteria with the modification that treatment-related lymphocytosis in the absence of other signs or symptoms of disease progression will not be considered progressive disease. The Investigator will evaluate sites of disease by radiologic imaging (primary), physical examination or other procedures as necessary, review of hematology and serum chemistry results, and disease-related symptoms. The same methods of assessment used to assess disease at baseline should be used throughout the study. A central laboratory will perform all hematology testing for the primary endpoint analysis. The primary efficacy analysis will be based on assessment from an IRC. As part of the IRC review, radiographic evaluations assessed by independent central radiologists and hematology results from a central laboratory will be provided. Detailed procedures will be described in a separate charter. An independent DMC will be formed and constituted according to regulatory agency guidelines. Detailed information regarding the composition of the DMC and detailed DMC procedures will be provided in a separate charter. The DMC will review the safety data periodically and provide recommendations according to the charter.

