7.2.2.1 Adverse Event Reporting Period

After the signing of the ICF and prior to the first dose of study drug, all SAEs must be reported.

After the first dose of study drug, all AEs/SAEs, irrespective of attribution of causality, must be reported.

All adverse events will be reported until 30 days after the last dose of study drug or the start of new anticancer therapy (whichever comes first). After this period, investigators should report serious adverse events or other adverse events of concern that are believed to be related to prior treatment with study drug.

All SAEs that occur during the reporting period should be followed to resolution or until the Investigator assesses the subject as stable or until the subject is lost to follow up or withdraws consent. Resolution/stable means the subject has returned to baseline state of health or the Investigator does not expect any further improvement or worsening of the event.

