#### **4.1.6 Treatment Emergent Period**

The treatment emergent period is defined as the period of time from the date of the first dose of study drug through 30 days after the date of the last dose of study drug or the first date starting new anticancer therapy for CLL, whichever is earlier.

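### SAP 8.1.2 runs events of clinical interest past progression with no cut-off for the by-arm tables, beyond the window in which the protocol collects adverse events completely

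*SAP*

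**What the plan says.** SAP 8.1.2 covers the ECIs defined in SAP Appendix 1, which include atrial fibrillation, ventricular tachyarrhythmias, cytopenias, hemorrhage, hypertension, infections and second primary malignancies. It has these events reported on treatment and in every follow-up period that the protocol sets, "including post-disease progression phase for overall survival". The next sentence is "These events will be summarized similarly to TEAEs by treatment arm". No cut-off, split by period or relatedness condition is attached to the tables.

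Protocol 7.2.2.1 sets the collection rule, irrespective of causality: "All adverse events will be reported until 30 days after the last dose of study drug or the start of new anticancer therapy", whichever is earlier. After that, "investigators should report serious adverse events or other adverse events of concern that are believed to be related to prior treatment with study drug".

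For the Post-disease Progression Phase, Protocol Section 4 lists subsequent therapy with its start date and indication, then "additional malignancy occurrence, and subject survival status will be recorded". Apart from additional malignancy, no ECI is in that list.

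SAP 4.1.6 defines the treatment-emergent period as running from first dose "through 30 days after the date of the last dose of study drug or the first date starting new anticancer therapy for CLL", taking the earlier of the two. This matches the protocol's window for complete collection.

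**The concern.** The SAP's reporting window for ECIs is longer than the period in which the protocol gathers adverse events completely. Once that period ends, most ECIs reach the database only if they are believed related to study drug. The trial is open-label (SAP 2.7.2) and the investigator judges relatedness (SAP 8.1). Whether a late bleed or a late episode of hypertension enters a by-arm table could therefore depend on how readily each drug is blamed.

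Two things are at stake. First, hemorrhage, hypertension and cytopenias are not tested endpoints, so the ECI tables are their dedicated comparison, and Protocol 2.2 presents a possibly distinct safety profile as something this trial can evaluate directly. Second, atrial fibrillation is both an ECI and a secondary endpoint under the same Appendix 1 definition, so the study report could carry two different counts of it.

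**Working it through.** No figure in the plan bears on this point, so the check is a comparison of texts.

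**1. The windows side by side**

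| Source | Governs | End of window | Filter |
|---|---|---|---|
| Protocol 7.2.2.1, main rule | Collection of all adverse events | Last dose + 30 days or new anticancer therapy, whichever is earlier | None |
| Protocol 7.2.2.1, later period | Collection after that | None stated | Serious events or other events of concern, believed related |
| Protocol Section 4 | Post-progression data | Death, loss to follow-up, consent withdrawal or study closure | Only listed items; malignancy is the one ECI among them |
| SAP 4.1.6 and 8.1.1 | Treatment-emergent events | Last dose + 30 days or new CLL therapy, whichever is earlier | None |
| SAP 8.1.2 | ECI reporting, then by-arm tables | All follow-up, including post-progression | None stated |
| SAP Appendix 2 | ECI narratives | Last dose + 30 days | Later: related serious events and clinically significant events as judged by the medical monitor |

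SAP 8.1.2 is the outlier. The protocol, the SAP's own treatment-emergent definition and the narrative rule all treat the later period differently from the on-drug period.

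**2. What the tables would contain.** The subject of the second sentence of 8.1.2 is the events just described, which run past progression. Read that way, each table adds together (a) all ECIs in the treatment-emergent period and (b) later ECIs that passed the filter. Part (a) is complete and part (b) is selective.

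**3. How they would be counted.** SAP 8.1.1 reports subjects with an event as a percentage of the safety population in each arm. If ECIs are handled likewise, a late, filtered event counts the same as an on-drug one, and nothing adjusts for unequal off-drug follow-up.

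**4. Atrial fibrillation.** SAP 7.2.1 tests treatment-emergent atrial fibrillation in the safety population, using Appendix 1. On the reading in step 2, in each arm:

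ECI count = endpoint count + subjects whose only qualifying event came after the treatment-emergent period and was reported.

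The two agree only if the last term is zero.

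**5. The tested endpoints.** SAP 7.2.1 and Protocol 9.6.2 place the treatment-emergent qualifier ahead of the list of Grade ≥3 infections, Richter's transformation and atrial fibrillation. The natural reading applies it to all three. The tables in 8.1.2 do not feed these tests.

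**6. Size.** This would need the number of late ECIs by arm and the off-drug follow-up by arm. The documents give neither.

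**The case against.** The strongest reply is that summarising ECIs in the manner of treatment-emergent events already imports the treatment-emergent window. SAP Section 8 bases the safety assessment on treatment-emergent events, Protocol 9.7 does the same, and Appendix 2 uses a last dose + 30 days window for ECIs. This reading is tenable. It is not stated, however, and the sentence just before it points the other way, so two programmers could reasonably produce different tables.

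Other parts of the reply stand as limits on the point:

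- **Not every late ECI depends on attribution.** Additional malignancy is recorded after progression without a causality filter. Ventricular arrhythmias are events of special interest under Protocol 7.2.2.3 and are reported irrespective of seriousness or causality, although that section sets no longer reporting period.
- **The later-period rule can be read two ways.** The relatedness clause in Protocol 7.2.2.1 most naturally covers both serious events and other events of concern, but it could apply only to the latter. Even then, late non-serious ECIs stay filtered.
- **Absence of collection cannot be proved from the schedule.** The post-progression column in Protocol Appendix A appears to carry a footnote whose text is redacted. Protocol 7.2.1 also speaks of adverse events up to the final study procedures, but that is a definition and sets no reporting period.
- **The rule is the same in both arms.** Realised follow-up may differ by arm, but so may time on treatment. Restricting the tables to the treatment-emergent period removes the selective ascertainment, not unequal exposure.

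A reader might also infer that infections would show the same double count as atrial fibrillation. The documents do not support that: the ECI is the whole infections class at any grade, while the tested endpoint is Grade ≥3, so those counts differ by design.

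**Conclusion.** SAP 8.1.2 is wrong as written: its reporting window does not fit the protocol's collection rule, and it gives no cut-off for the tables. The severity is minor. On the natural reading, the descriptive by-arm ECI tables combine complete data with data filtered by unblinded causality judgment, and the atrial fibrillation count may not match the endpoint.

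A reader might infer that the gatekept safety comparisons are compromised, or that the tables favour one drug. Neither follows. The tested endpoints are treatment-emergent, the primary analysis and the treatment-emergent event tables do not depend on 8.1.2, and 8.1.2 attaches no test or decision rule to the ECI tables. The size and direction of any distortion are unknown.

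The conclusion assumes that the ECI tables are not silently limited to the treatment-emergent period, and that no redacted text extends complete ECI collection past the window in Protocol 7.2.2.1.

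**What to change.** In SAP 8.1.2:

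- State that the by-arm ECI tables cover the treatment-emergent period of Section 4.1.6 only.
- Put later ECIs in a separate listing, labelled as incompletely collected and without a between-arm comparison.
- Summarise second primary malignancies over full follow-up as an analysis of their own. Protocol Section 4 names additional malignancy for the post-progression phase but not in its description of the Post-treatment Phase, so say what was collected between the end of the adverse event window and progression.
- Reconcile the reporting sentence with Protocol 7.2.2.1. If longer collection of ECIs was intended, the protocol has to say so.

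No change to SAP 7.2.1 is needed. The cost is SAP wording and one listing, with no new data collection.

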### **8.1.3 Adverse Events of Special Interest**

Adverse events of special interest (AESIs) differ from ECIs in that they must be reported to the sponsor expeditiously and are defined according to Appendix 1. AESIs will be summarized similarly to TEAEs by treatment arm.

### **8.1.4 Subgroup Analyses for Adverse Events**

Subgroup analyses will be performed for TEAEs using the same subgroups used for the primary endpoint subgroup analyses (listed in Section 7.1.4) to investigate benefit:risk for acalabrutinib versus ibrutinib.

For each of the TEAE types listed below, the risk difference (Arm A – Arm B) and its corresponding 95% CI for each subgroup will be calculated based on normal approximation (with use of Wilson's score) and displayed graphically in a forest plot. Additional subgroups may be considered as appropriate.

- Grade  $\geq 3$  TEAEs
- TEAEs leading to dose interruption
- TEAEs leading to discontinuation of treatment

## **8.2 Deaths**

All reported deaths will be summarized by treatment arm and cause of death. A by-subject listing that includes date of death and cause of death will be provided.

## **8.3 Laboratory Assessments**

### **8.3.1 Data Processing Methods**

All laboratory values will be converted to and reported as SI units and classified as normal, low, or high based on the normal ranges provided by the central laboratory. In general, only data from the central laboratory will be summarized and analyzed. Hematologic parameters, including platelet counts, hemoglobin, and neutrophils, will be assessed by the grading scale for hematologic toxicity in CLL studies with use of both the IWCLL 2008 guidelines and NCI CTCAE v4.03. All other gradable laboratory parameters will be graded using the NCI CTCAE v4.03.

Per the grading scale in the IWCLL guidelines, 1) ANC: Both baseline grade and post-baseline grade are defined based on absolute values, and (2) hemoglobin and

platelet: baseline grade is not applicable (no criterion is provided to define baseline grade), and post-baseline grade is based on percentage decrease from baseline value.

Gradable parameters that have criteria available for both low and high values (e.g., hypercalcemia for a high value of calcium and hypocalcemia for a low value of calcium) based on the NCI CTCAE v4.03 will be summarized for both criteria (low and high).

Subjects will be counted only once for each criterion/direction. The same subject can be counted for both criteria if the subject has laboratory values that meet each criterion.

Subjects who meet the criteria for Grade 1 or higher for the high direction will be summarized under Grade 0 for summarization of the low direction and vice versa.

Change from baseline to post-baseline value will be calculated for each parameter.

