9.7 SAFETY ANALYSES

Safety data will be summarized for the safety population. The baseline value for safety analysis is defined as the value collected at the time closest to and before the start of study drug administration.

Adverse Events

AEs will be graded by the investigator according to the National Cancer Institute (NCI) CTCAE v4.03 or higher for non-hematologic AEs. Hematologic toxicity will be assessed by the grading scale for hematologic toxicity in CLL studies in the IWCLL 2008 guidelines. Each AE verbatim term will be coded to a system organ class and a preferred term using the Medical Dictionary for Regulatory Activities (MedDRA).

Treatment-emergent Adverse Events

All TEAEs will be summarized by treatment arm as treated. In addition, AE incidence rates will also be summarized by severity and relationship to study drug.

Grade 3 or Grade 4 TEAEs; TEAEs leading to permanent study drug treatment discontinuation; TEAEs leading to dose reduction; serious TEAEs; TEAEs of special interest and TEAEs resulting in death will be summarized by treatment arm as treated.

Clinical Laboratory Tests

Data Summary Methods:

For gradable parameters, a summary of worst post baseline toxicity grade will be provided in the treatment-emergent period and worst toxicity grade (any grade and Grade 3/4). The difference between groups in percentages will be displayed.

Liver function abnormality by Hy's law and frequencies of abnormal treatment emergent uric acid will be summarized.

Analysis of Lymphocytosis:

For all subjects with baseline and any post-baseline ALC measurements, ALC at peak summary will be provided by treatment arm. *Median percentage change in ALC from baseline with its 95% CI will also be displayed graphically over time.*

CCI [Redacted]
[Redacted]
[Redacted] CCI [Redacted]
[Redacted]

CCI [Redacted]
[Redacted]
[Redacted]
[Redacted]
[Redacted]
[Redacted]
[Redacted]

CCI [Redacted]
[Redacted]
[Redacted]
[Redacted]
[Redacted]

ECOG Performance Status

ECOG performance status will be collected as scheduled in [Appendix A](#). ECOG performance status grade ranges from 0 to 5. Descriptive statistics will be provided for each visit over time.

Vital Signs and Weight

Body temperature, heart rate (beats/min), systolic blood pressure (mmHg), diastolic blood pressure (mmHg), respiratory rate (breaths/min), and weight will be collected as scheduled in [Appendix A](#). For each parameter, descriptive statistics will be provided over time.

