### **8.3.2 Analysis of Treatment Emergent Clinical Laboratory**

Subject incidence of hematologic toxicities for platelet counts, hemoglobin, and neutrophils, graded per IWCLL 2008 guideline and CTCAE, will be summarized by treatment arm and grade.

The treatment emergent laboratory abnormality is defined as laboratory abnormality reported during the treatment emergent period (defined in Section 6). Treatment emergent laboratory abnormality, per NCI CTCAE v4.03 grading, will be summarized for hematology and chemistry laboratory parameters of clinical interest.

Shift from baseline grade to maximum post-baseline CTCAE grade will be summarized for hematology and chemistry laboratory parameters of clinical interest.

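### SAP 8.3.1 gives two adjacent counting rules that conflict for subjects with graded laboratory values in both directions; followed literally, the second reports such a subject as Grade 0 twice

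*SAP*

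**What the plan says.** SAP 8.3.1 (Data Processing Methods) deals with "Gradable parameters that have criteria available for both low and high values", with calcium as its example, and has them summarized in each direction. Three counting statements follow:

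- Within a direction: "Subjects will be counted only once for each criterion/direction".
- Across directions: "The same subject can be counted for both criteria if the subject has laboratory values that meet each criterion".
- Then: "Subjects who meet the criteria for Grade 1 or higher for the high direction will be summarized under Grade 0". The table meant here is the low-direction one, and the opposite case is treated alike.

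Two places describe the tables built on these grades. Protocol 9.7, under clinical laboratory tests, states: "For gradable parameters, a summary of worst post baseline toxicity grade will be provided in the treatment-emergent period"; it adds that the between-group difference in percentages is to be shown. SAP 8.3.2 states: "Shift from baseline grade to maximum post-baseline CTCAE grade will be summarized for hematology and chemistry laboratory parameters of clinical interest".

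**The concern.** The third statement takes the subject as its unit. It is not limited to a single value, to a visit, or to subjects abnormal in one direction only. For a subject with post-baseline Grade 1 or higher values in both directions it cannot be followed together with the second statement. Because it runs both ways, such a subject drops to Grade 0 in both tables.

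This situation can plausibly arise. Calcium is in the serum chemistry panel (Protocol 7.1), chemistry is repeated during treatment (Protocol Appendix A), and treatment continues until progression or unacceptable toxicity. A worst grade taken over many visits can meet both criteria.

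At stake is whether the laboratory tables report the worst grade that Protocol 9.7 calls for. Laboratory assessments are part of the stated safety objective. Two programmers could each follow this section faithfully and produce different tables.

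**Working it through.** The plan states no figure on this point, so there is none to reproduce. The check compares the two rules on examples and then sizes the difference under assumed rates.

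**Step 1: apply both rules to three subjects.** Grades are written as (worst low, worst high).

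| Subject | True grades | Counting in both directions allowed | Grade 0 sentence, literal |
|---|---|---|---|
| X, low only | (3, 0) | (3, 0) | (3, 0) |
| Y, high only | (0, 2) | (0, 2) | (0, 2) |
| Z, both | (3, 1) | (3, 1) | (0, 0) |

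The rules agree for X and Y. They differ only for Z, who disappears from both tables.

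**Step 2: formula for the loss.** Let pL and pH be the proportions of subjects ever at Grade 1 or higher in the low and high directions, and pB the proportion with both. Under the literal rule:

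- reported low = pL − pB
- reported high = pH − pB

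The loss is pB in each direction. If the two directions are independent, pB = pL × pH. For the rates below, pB can lie anywhere from 0 (no overlap) to the smaller of pL and pH (full overlap).

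**Step 3: numbers.** The rates and the independence are assumptions, because the documents give no laboratory rates. The 250 per arm is the planned randomized number (SAP 2.1); the safety population may be slightly smaller.

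| pL | pH | pB if independent | Reported low | Reported high | Subjects lost per direction, per 250 | Range of pB |
|---|---|---|---|---|---|---|
| 10% | 10% | 0.10 × 0.10 = 1% | 9% | 9% | 2.5 | 0 to 10% |
| 20% | 30% | 0.20 × 0.30 = 6% | 14% | 24% | 15 | 0 to 20% |
| 30% | 40% | 0.30 × 0.40 = 12% | 18% | 28% | 30 | 0 to 30% |

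**Step 4: can the loss differ by arm?** Suppose the true low rate is 20% in both arms, the high rate is 10% in one and 30% in the other, and the directions are independent. Reported low rates are 0.20 × (1 − 0.10) = 18% and 0.20 × (1 − 0.30) = 14%. This is an artificial difference of 4 points. It needs the arms to differ in the opposite direction's rate, and the documents give no evidence on that.

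**Step 5: where the sentence is correct.** SAP 4.1.1 defines the safety baseline as the last measurement before first dose. A single value cannot be both high and low, so Grade 0 in the opposite direction is right at baseline. It is also right for any subject abnormal in one direction only. The conflict is confined to post-baseline grades of subjects abnormal in both.

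**The case against.** The strongest reply is that the section can be read consistently. On that reading, the sentence allowing a subject to count in both directions covers subjects like Z. The Grade 0 sentence then only places everyone else: a subject abnormal in the high direction alone stays in the low-direction table at Grade 0 and is not dropped. This gives effect to both sentences, whereas the literal reading leaves the first with none. The worst-grade and maximum-grade wording in Protocol 9.7 and SAP 8.3.2 points the same way.

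This is probably what the authors meant. However, the restriction to one-direction subjects, or to single values, has to be supplied by the reader. Neither document says which sentence governs, and a data-processing rule should not yield a wrong table when followed as written.

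The reply succeeds in limiting the consequence. A reader might infer that the SAP erases laboratory toxicity outright. The documents do not support that:

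- The loss occurs only under literal programming.
- Laboratory abnormalities that need treatment or a change in study drug are adverse events (Protocol 7.2.1) and are tabulated by severity (SAP 8.1.1).
- Change from baseline is still calculated for every parameter (SAP 8.3.1).
- IWCLL grading of platelets, hemoglobin and neutrophils covers decreases only (Protocol Appendix E) and is untouched.

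A reader might also infer bias from unequal treatment duration, or a loss concentrated in subjects with the most unstable chemistry. The documents give no duration by arm. Two mild excursions at different visits trigger the rule as readily as severe ones.

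**Conclusion.** The conflict is real and narrow. For two-way CTCAE parameters, a subject with post-baseline Grade 1 or higher values in both directions is counted in both tables by one sentence and in neither by the next. The second rule is wrong as written, although its likely intent is sound.

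If it is programmed literally, each direction loses the share of subjects abnormal in both. That share is not in the documents. The illustrations of 1, 6 and 12 points rest on assumed rates and independence, and the true loss may be zero. If it is programmed as probably intended, nothing is lost.

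The affected outputs are descriptive. No laboratory grade enters the PFS non-inferiority test or the hierarchy of secondary endpoints in SAP 2.6. This is a minor correction, but one worth making before the tables are programmed.

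**What to change.** Replace the Grade 0 sentence in SAP 8.3.1 with:

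*For each laboratory value, a Grade ≥ 1 result in one direction is Grade 0 for the opposite direction. A subject's worst post-baseline grade is derived separately per direction over all values in the treatment-emergent period, so a subject may have Grade ≥ 1 in both; a subject with no Grade ≥ 1 value in a direction is summarized under Grade 0 for that direction.*

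This keeps the sentence that lets a subject count in both directions, agrees with the worst-grade summary in Protocol 9.7, and leaves subjects abnormal in one direction unchanged. The shift tables in SAP 8.3.2 should use the same per-direction derivation.

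The cost is a change to one sentence of the SAP and a check that the table programs follow it. It needs no new data and no additional tables.
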